extent of tumor volume, tumor motion and patient anatomy variation during radiation treatment.

While tumor anatomic changes are important in radiation treatment with photon therapy, these factors are of particular concern when implementing proton therapy. Unlike photon beams, proton beams can deliver radiation that enters the body at low doses, but then uniformly delivers high doses of radiation to the tumor followed by a steep fall-off exit dose. These features allow high doses of radiation to be delivered to the primary tumor, with lower toxicity to normal tissue. Because of the sharp demarcations between low dose and high dose areas, proton therapy requires accurate delineation of the primary tumor in order to deliver adequate radiation dose to the tumor while limiting normal tissue toxicity. Therefore, adjusting for anatomic changes in tumors during radiation treatment is particularly important in proton therapy. Hui et al. studied the effect of anatomic changes on proton therapy dose distribution in lung cancer using weekly 4D CT Scans. Although only 8 patients were examined, there was variation in the CTV density as radiation treatment progressed. The authors concluded, however, that CTV coverage is adequate if tumor motion is taken into consideration with 4D CT planning. Interestingly, this CTV density variation was correlated with normal tissue toxicity, implying that as the tumor shrinks from radiation treatment, the high dose radiation spills over to normal tissue. The secondary objective of our study will be to utilize the serial imaging obtained from either the photon beam or proton beam patients to generate serial proton beam plans. This will allow us to estimate the dosimetric error with proton beam radiotherapy if tumor and patient anatomical changes are not accounted for during treatment.

We propose to quantify the changes in tumor volume, motion, and anatomic changes that occur during the time course of definitive radiotherapy in patients with lung cancers, head and neck cancers, gastrointestinal cancers (including but not limited to colorectal and rectal cancers) and gynecological cancers. These cancers were chosen as they represent the oncologic subsets that experience the greatest dynamic range in these variables during treatment.

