### 3.0 SPECIFIC AIMS/OBJECTIVES

**Specific Aim 1:** To estimate the degree of tumor volume, tumor motion and patient anatomy change during treatment with photon beam radiotherapy.

- 1a. To estimate the degree and impact of tumor volume change during the course of definitive photon radiotherapy treatment in lung cancers, head and neck cancers, gastrointestinal cancers (including but not limited to colorectal and rectal cancers) and gynecological cancers.
- 1b. To estimate the degree and impact of tumor motion (anatomic location) change during the course of definitive photon radiotherapy treatment in lung cancers, head and neck cancers, gastrointestinal cancers (including but not limited to colorectal and rectal cancers and gynecological cancers).
- 1c. To estimate the degree and impact of changes in patient anatomy during the course of definitive photon radiotherapy treatment in head and neck and upper gastrointestinal cancers.

Hypothesis: Tumor volume and motion will change over the course of radiation treatment in patients with lung cancers, head and neck cancers, gastrointestinal cancers (including but not limited to colorectal and rectal cancers) and gynecological cancers. The weight loss experienced by patients with upper gastrointestinal and head and neck cancers will have a significant impact on their anatomy. These changes will alter the dose distribution of the photon beam treatment plans, possibly limiting radiation dose delivery to the target volumes and increasing radiation toxicity to surrounding critical structures.

**Specific Aim 2:** To estimate the error if tumor volume, tumor motion and patient anatomy change during treatment with proton beam radiotherapy.

- 2a. To generate simulated proton beam plans using serial CT or MR imaging obtained from either photon or proton beam patients to estimate the dosimetric error if these changes are unaccounted for during proton treatment.

[figure not shown]
Hypothesis: The changes in tumor volume and motion and patient anatomy will have a greater effect on appropriate dose distribution in plans using proton beam therapy compared to photon beam therapy given the need for more accurate target delineation in proton beam therapy.

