## **9.0 STATISTICAL CONSIDERATIONS**

### **9.1 *Background:***

Tumor volume, location and proximity to critical normal organs are determined by CT scans prior to the start of radiation treatment. Radiation dosimetry plans are not re-calibrated during the course of a patient's treatment since it is assumed that changes in these variables are negligible. This hypothesis has rarely been studied in a rigorous manner. Dramatic tumor shrinkage or patient weight loss, may cause the radiation energy beam to over-shoot the treatment target and may also increase the radiation dose to nearby critical normal organs.

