**9.5 Plans for Data Analysis: To be conducted within each stratum**

1. Tumor Volume: To determine the distributions of volume variables and percent change from baseline. At each scan time point, compute mean, median, range and standard deviation of these variables and plot mean values over time. To compare volume variables at baseline to the values at selected scan time points by paired Wilcoxon signed ranks test.
2. Tumor Motion: At each scan time point, compute mean, median, range and standard deviation of the dose coverage and plot mean values over time. To compare ITV or CTV variables at baseline to the GTV at selected scan time points by paired Wilcoxon signed ranks test.
3. Patient Anatomy: To determine the distribution of patient percent weight loss. At each scan time point, compute mean, median, range and standard deviation of percent weight loss and plot mean values over time.
4. Dose distribution: To determine the distributions of radiation dose to GTV, ITV and critical normal organs. To correlate radiation dose to normal organs with percent weight loss.
5. Conduct exploratory longitudinal analyses to examine changes over time in the 30 patients. Random effects linear regression models will be employed to estimate changes in variables over time clustered by patient. Natural log transformation will be applied prior to modeling.
6. To assess if changes in volume variables are clinically relevant and if so, identify the earliest time point at which re-calibration is warranted. Although it may not be possible to identify a single 're-calibration solution' for all patients in a particular stratum, we will attempt to identify the earliest scan time point at which the majority of patients have clinically important changes in tumor volume or location resulting in over-shoot of the target volume and/or increased dose exposure to normal organs.

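### Section 9.5 item 4 attributes organ-dose change to weight loss without accounting for tumor shrinkage over the same weeks, so the correlation can credit weight loss with an effect that is not its own

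*Combined protocol and SAP*

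**What the plan says.** Aim 1c in Section 3.0 is "To estimate the degree and impact of changes in patient anatomy during the course of definitive photon radiotherapy treatment", for head and neck and upper gastrointestinal cancers. Aim 1a asks the corresponding question about tumor volume separately. The hypothesis under Aim 1 singles out weight loss in those two groups.

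The analyses that could serve Aim 1c are in Section 9.5, to be run within each stratum of 30:

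- Item 3: "Patient Anatomy: To determine the distribution of patient percent weight loss", summarised at each scan. It makes no link to dose.
- Item 4: distributions of dose to GTV, ITV and normal organs, then "To correlate radiation dose to normal organs with percent weight loss". No covariate, scan, change definition or type of correlation is stated.
- Item 5: "Random effects linear regression models will be employed to estimate changes in variables over time clustered by patient". This models variables against time. No model of dose on weight loss and tumor volume together is described.
- Item 6: looks for "clinically important changes in tumor volume or location resulting in over-shoot of the target volume and/or increased dose exposure to normal organs". Weight is not mentioned.

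On causes, Section 9.1 states "Dramatic tumor shrinkage or patient weight loss, may cause the radiation energy beam to over-shoot the treatment target" and adds that this "may also increase the radiation dose to nearby critical normal organs". Section 2.0 describes a cited eight-patient proton lung study as implying that "as the tumor shrinks from radiation treatment, the high dose radiation spills over to normal tissue".

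Section 9.4 schedules GTV, weight and organ dose at baseline and then weekly.

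**The concern.** The protocol names two processes that may raise organ dose, and both advance with treatment. Section 6.6 re-applies the initial plan to each new scan, so the recorded organ dose reflects whatever shrinkage, displacement and weight loss are present at once. Correlating that dose with one of the processes and leaving out the other lets the first stand in for the second.

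This can happen in two ways. At one scan, patients whose tumors shrink faster may also lose more weight, and a shrinkage effect then appears as a weight-loss effect. If several scans per patient are pooled, both variables rise with week, and the common trend produces a correlation even when the two rates are unrelated between patients. Item 4 does not say which form is intended.

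At stake is the attribution under Aim 1c: a stratum report could name weight loss as the driver of organ dose when shrinkage, or elapsed time, explains the association. Section 9.2 says the study will inform decisions on whether and when to re-calibrate plans, so the description should point to the right process.

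**Working it through.** **The plan's own figure.** 30 patients × 4 strata = 120, which agrees with the stated total. No power, alpha or effect size is given, and no figure is attached to the dose and weight-loss correlation, so there is nothing further to reproduce.

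**Size of the two processes in the documents (Section 2.0).** GTV reduction is 69.5% by end of treatment in head and neck cancer and a median of 44.3% at 50 Gy in NSCLC. About 35% of head and neck patients lose more than 10% of their weight. The documents give neither the between-patient correlation of weight loss with shrinkage nor the correlation of organ dose with shrinkage. Both must be assumed.

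**Single scan, closed form.** If weight loss has no effect on dose, then

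r(dose, weight loss) = r(weight loss, shrinkage) × r(dose, shrinkage).

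With n = 30, two-sided 5% critical |r| = 0.36, and 20,000 runs per row:

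| r(weight loss, shrinkage) | r(dose, shrinkage) | Product | Simulated mean r | Nominal p < 0.05 |
|---|---|---|---|---|
| 0 | 0.5 | 0 | 0.00 | 5% |
| 0.3 | 0.3 | 0.09 | 0.09 | 8% |
| 0.3 | 0.5 | 0.15 | 0.15 | 12% |
| 0.5 | 0.5 | 0.25 | 0.25 | 27% |
| 0.5 | 0.7 | 0.35 | 0.35 | 49% |

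The partial correlation given shrinkage averages about 0.00 in every row.

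**Single scan, explicit weekly model.** Assumptions: 30 patients, 7 weekly scans, 4,000 strata per setting. The weight-loss slope is N(1.1, 0.6) % per week and the log-GTV slope N(0.117, 0.06) per week. Measurement noise has SD 0.7% for weight and 0.10 for log-GTV. Dose change is 8% at full shrinkage plus noise, with no weight-loss term. Plausibility at week 7: mean weight loss is 1.1 × 7 = 7.7%, and shrinkage at the mean slope is 1 − exp(−0.117 × 7) = 1 − 0.44 = 56%, between the two cited GTV figures.

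- Dose-noise SD 1%, rate correlations 0.2, 0.3 and 0.5: mean r = 0.16, 0.24 and 0.40. After adjustment for measured GTV change: 0.01 to 0.05.
- Rate correlation 0.3, dose-noise SD 1%, 3% and 5%: mean r = 0.24, about 0.14 and 0.09.
- Lowest corner (rate correlation 0.2, SD 5%): 0.06.
- Rate correlation 0: about 0.

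**Scans pooled, rates unrelated between patients.** Same model, SD 1%:

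| Adjustment | Mean r |
|---|---|
| None | 0.36 (95% range 0.14 to 0.55) |
| GTV change only | 0.07 |
| Week only | 0.003 |
| GTV change and week | 0.002 |

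At SD 5% the unadjusted pooled r is 0.13. A second set of assumptions (mean weight loss 8%, mean shrinkage 60%, dose-change SD 4 to 8 points) gives 0.17 to 0.40 with 3 scans and 0.20 to 0.44 with 7. Here the artefact is the time trend, and week is the term that removes it.

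**Scans pooled, rates correlated 0.5, SD 1%.** Adjusting for GTV alone leaves r = 0.14. Adding week brings it to about 0.10, because GTV is measured with error.

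**Precision in one stratum.** For an observed r of 0.25 at n = 30, Fisher z = 0.255 ± 1.96/√27 = 0.255 ± 0.377, giving a 95% CI of −0.12 to 0.56.

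**The case against.** Four arguments on the other side have force.

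First, a reader might infer that anatomy impact is not otherwise assessed. That goes too far. Re-applying the initial plan to each scan measures the combined dosimetric effect of all changes, and the first part of item 4 reports it. What is missing is attribution to weight loss.

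Second, a reader might take it as established that shrinkage raises organ dose. Section 9.1 says only that it may. The Section 2.0 statement is an inference from eight proton lung patients, whereas Aim 1c concerns photon treatment of other sites. The confounding is therefore possible on the protocol's own premises, not demonstrated.

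Third, the pooled correlation might be read as proof that a GTV term is needed. It is not: week alone removes it when the rates are unrelated. Nothing in item 4 says that scans will be pooled, and items 1 to 3 are summarised scan by scan. The single-scan bias needs an assumed between-patient correlation and shrinks as dose noise grows.

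Fourth, Section 9.2 calls the study descriptive and not powered, and item 4 specifies no test. The nominal significance percentages above are a yardstick, not error rates of a planned test. Item 6 also does not use this correlation in its re-calibration judgement.

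All four limit the size and reach of the point. None supplies an analysis that separates weight loss from shrinkage, and a descriptive aim does not protect a correlation from being read as attribution when Aim 1c asks for impact.

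**Conclusion.** The point stands in modest form. Item 4 is the only planned analysis that attributes organ-dose change to weight loss, and it omits a second process that the protocol itself says may raise organ dose over the same weeks. The result can misattribute a shrinkage effect, or a shared time trend if scans are pooled, to weight loss.

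The size cannot be determined from the documents. With no true weight-loss effect and n = 30, the single-scan r is about 0 if the rates are unrelated between patients, and about 0.06 to 0.40 for assumed rate correlations of 0.2 to 0.5 and dose-noise SDs of 1% to 5%. Pooling gives about 0.13 to 0.36 from the time trend alone over the same noise range. These figures rest on the assumed 8% dose effect at full shrinkage and the assumed slopes.

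The documents do not support concluding that any weight-loss association found will be spurious, or that re-planning conclusions would necessarily be wrong. The harm is a possibly misleading answer to Aim 1c. The improvement is worth making because it uses data already scheduled.

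**What to change.** Replace the correlation sentence in Section 9.5 item 4 with:

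*Model change from baseline in normal-organ dose on percent weight loss and percent GTV change together, either at a fixed scan time point or across scans with a term for week and a random patient effect; report the weight-loss coefficient with its 95% CI as exploratory, with the unadjusted correlation beside it.*

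The week term is essential if scans are combined, because GTV change alone does not fully remove the shared time trend.

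The cost is one sentence. GTV, weight and organ dose are already on the same schedule, and item 5 already plans random-effects regression. The interval will be somewhat wider when the two predictors are correlated. Some residual confounding will remain from GTV contouring error and from tumor displacement, which the model does not include, so the coefficient should not be presented as an isolated causal effect of weight loss.

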### **9.2 *Study Design:***

This pilot study will determine changes over time in tumor volume and motion and patient anatomy, as well as dose distributions to normal organs. The study will inform medical decision-making about the need for (and timing of) re-calibration of radiation dosimetry plans. Up to weekly CT and/or serial MR scans (minimum of 3) will be employed to measure changes in tumor volume and motion and patient anatomy in patients receiving definitive radiation therapy (with or without concurrent chemotherapy). This study is not designed to evaluate the CT or MR procedure. CT or MR is simply the imaging method used for precise measurement of tumor volume variables. Enrollment will be stratified by disease site: NSCLC, Head & Neck, GI and Gynecologic tumors. The study will enroll 30 patients in each stratum. This study is descriptive and not powered hypothesis testing.

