### **9.3 *Objectives:* To determine changes over time in:**

1. tumor volume variables
2. tumor motion
3. patient anatomy
4. dose distribution to tumor and critical normal organs

**9.4 Endpoints:** To be measured at baseline and then weekly during 7-8 weeks of radiotherapy

1. GTV (gross tumor volume), the volume of the primary tumor visualized on the CT scan
2. ITV (interior tumor volume), the GTV expanded to include interior motion (i.e., breathing or swallowing) such that the tumor resides within the ITV during normal motion
3. CTV (clinical tumor volume), the ITV expanded to include microscopic disease (margins)
4. PTV (planning tumor volume), the CTV expanded by several mm, as determined by radiation dosimetry planning, PTV is considered the ultimate target volume

NOTE the relationship: GTV < ITV < CTV < PTV

5. Dose coverage: at each scan time point, determine the percent of the GTV which resides within the baseline ITV or CTV
5. patient weight and percent weight loss from baseline
6. Radiation dose to critical normal organs based on dose-volume histograms (i.e., 20 Gy to 50% of normal lung tissue)

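### Does the unrestricted natural log in section 9.5, item 5, leave outcomes that cannot be modelled?

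*Combined protocol and SAP*

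**What the plan says.** Section 9.5 is carried out within each disease stratum of 30 patients. Item 5 reads: "Conduct exploratory longitudinal analyses to examine changes over time in the 30 patients". It continues: "Random effects linear regression models will be employed to estimate changes in variables over time clustered by patient". The third sentence is "Natural log transformation will be applied prior to modeling". Item 5 names no outcomes and gives no rule for zero or negative values.

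The other items say what is summarised without a log. Item 1 aims: "To determine the distributions of volume variables and percent change from baseline". Item 3 covers patient anatomy: "At each scan time point, compute mean, median, range and standard deviation of percent weight loss and plot mean values over time".

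Section 9.4 lists the endpoints: four volumes (GTV, ITV, CTV, PTV), dose coverage, organ dose, and "patient weight and percent weight loss from baseline". The endpoints are "To be measured at baseline and then weekly during 7-8 weeks of radiotherapy", while section 9.2 describes the imaging as "Up to weekly CT and/or serial MR scans (minimum of 3) will be employed". Section 9.2 also calls the study descriptive and not powered for testing.

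**The concern.** A natural log needs a value above zero. Percent change in volume is zero at baseline and negative whenever the tumour shrinks, which is what the protocol expects. Percent weight loss is zero at baseline and zero or negative at any visit without loss. Section 2.0 itself gives a gastrointestinal range that starts at 0%.

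Item 5 follows items on volume, motion, anatomy and dose, and it says only variables where items 1 and 6 say volume variables. It can therefore be taken to cover everything before it. Percent weight loss is the only anatomy quantity that item 3 summarises, so someone modelling anatomy might well choose it.

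If it were logged, software would discard the records without loss and keep the rest. Missingness would then depend on the outcome, for the endpoint behind Aim 1c and the weight-loss hypothesis in section 3.0. Two analysts could also fit different models to different sets of records.

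**Working it through.** **1. Where the log exists.** Inputs are the changes cited in section 2.0.

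| Quantity | Value | ln of the percentage itself | ln of the ratio to baseline |
|---|---|---|---|
| GTV change, NSCLC (median) | -44.3% | undefined | ln(0.557) = -0.585 |
| GTV change, head and neck | -69.5% | undefined | ln(0.305) = -1.187 |
| Cervix, chemoradiation | -79% | undefined | ln(0.21) = -1.561 |
| Weight loss, GI lower end | 0% | undefined | ln(1.00) = 0 |
| Weight loss, GI upper end | 12% | ln(12) = 2.485 | ln(0.88) = -0.128 |
| Weight gain (assumed example) | 2% | undefined | ln(1.02) = +0.020 |

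The raw measures pose no difficulty, and the ratio converts back exactly to percent change: 100 × (exp(-0.585) - 1) = -44.3%. The difficulty arises only if a percentage is logged. Even then it concerns values at or below zero: shrinkage coded as a positive percent reduction has a log at every visit except baseline.

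**2. How visible a misapplication would be.** Baseline plus 7 or 8 weekly records gives 8 or 9 per patient. Baseline is always zero on either percentage, so 30 of 240 (12.5%) or 30 of 270 (11.1%) records per stratum fail at once. For signed GTV change, a median of -44.3% puts at least half of patients below zero: at least 15 of 30, if the NSCLC stratum resembled that series.

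**3. Follow-up records lost if percent weight loss were logged.** This is an illustration. From the documents: about 35% of head and neck patients lose more than 10% (section 2.0), 30 patients, weekly measurement, a minimum of three MR scans. Assumed: end-of-treatment loss normal with mean m and SD s, linear over 7 weeks, visit noise SD 1 point, three scans at weeks 2, 4 and 6.

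From P(loss > 10) = 0.35, m = 10 - 0.3853 × s.

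P(loss ≤ 0 at week w) = Φ( -(w/7) × m / √((w/7)² × s² + 1) ).

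| s | m | Week 1 | Week 7 | Mean, weeks 1-7 (of 210 records) | Mean, three scans (of 90 records) |
|---|---|---|---|---|---|
| 3 | 8.84 | 12.3% | 0.3% | 2.5% (about 5) | 1.2% (about 1) |
| 4 | 8.46 | 14.7% | 2.0% | 4.7% (about 10) | 3.4% (about 3) |
| 5 | 8.07 | 17.4% | 5.7% | 8.2% (about 17) | 7.2% (about 6) |
| 6 | 7.69 | 20.2% | 10.3% | 12.5% (about 26) | 11.6% (about 10) |

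At s = 3, week 1 supplies 12.3 / (7 × 2.5) = about 70% of the lost share. That figure is largely the assumed 1-point noise set against a small early loss.

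**4. Which reading the text supports.** Section 9 uses the word variables mainly for tumour measures: tumour volume variables in 9.2 and 9.3, volume variables in 9.5 items 1 and 6, ITV or CTV variables in item 2. Items 3 and 4, on weight loss and dose, do not use it. Item 5 estimates change over time through a regression on time, so the slope is the change and the natural response is the measured value, not a quantity already differenced from baseline. On the log scale that slope is a proportional change, which is a good reason for taking the log. For anatomy, body weight is itself a listed endpoint and is always positive.

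**The case for a change.** The best argument for an edit is that item 5 drops the qualifier its neighbours use, and that the weight-loss failure is partial. Some records yield a log and others disappear, and those that disappear share the outcome value of no loss. The illustrative loss falls mostly on early visits, and item 6 looks for the earliest time at which most patients have important changes. A line or two of text would remove the doubt at no cost in patients or scans.

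Part of this stands. The outcomes are not listed, and a literal reading is possible. A complete list would also have to cover dose coverage, organ dose and a GTV of zero after complete regression, each of which can be zero in principle.

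The rest does not carry through. The baseline zeros make the problem plain before any follow-up record is considered. Item 6 does not rest on the log model. The patient-anatomy objective is answered by item 3, on the untransformed scale. No direction of bias can be claimed either: dropping records without loss raises the fitted value, back-transforming to a geometric mean lowers it, and a straight line on the log scale misfits a linear trajectory. The 0-12% range is weak evidence of frequent zeros, because the text does not say whether 0 is an individual or a study-level value, or at what time it applies.

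**Conclusion.** No change is needed. The wording is loose, but the reading that fits the rest of section 9 and the purpose of the model is sound: log the raw volumes and body weight, and read the slope as a proportional change. On that reading no record is lost, apart from a GTV of zero, for which the documents give no rate. On the literal reading, the loss for head and neck weight loss would be about 2.5% to 12.5% of weekly follow-up records, or 1.2% to 11.6% with three scans. Those figures rest on the assumed SD, linearity, normality, visit noise and scan weeks; only the 35%, the 30 patients and the schedule come from the documents. A competent analyst would not go on logging zero or negative percentages once every baseline record failed. Item 5 is exploratory in a descriptive study, items 1 to 3 use no log, and no wrong result has been shown to follow.

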**REQUIRED SAMPLE SIZE**

- 30 patients per treatment site for a total of 120 patients.

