## Quantification of Tumor and Organ at Risk (OAR) Volume and Motion Path Changes during Definitive Photon or Proton Beam Radiotherapy

respiratory motion when calculating appropriate target volume margins. The distal esophagus can move 0.8cm radially and 1.8cm axially (Yaremko) and the pancreas can move 2.4 +/- 1.6 cm axially (Bussels). Lung tumors are significantly affected by respiratory motion and move 5-10 mm during quiet breathing and as much as 4.5 cm (Stevens) with deeper breaths. Therefore, accounting for respiratory motion can be extremely important for targeted radiation therapy.

The course of radiation treatment often lasts longer than 8 weeks. For patients with head and neck and gastrointestinal cancers, maintaining adequate nutrition during this time can be challenging. Studies have shown that about 35% of patients with head and neck cancers experience >10% weight loss and patients with gastrointestinal cancers experience weight loss ranging from 0-12% (Milano, Talamonti, Lin). Significant weight loss results in changes in patient anatomy, which can distort radiation dose distribution and therefore treatment efficacy.

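### Section 9.5 item 6 asks when re-calibration first becomes warranted but scores it by majority, so a stratum with up to half its patients changed names no scan, and a named scan can come late for up to half

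*Combined protocol and SAP*

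**What the plan says.** Section 9.2 gives the purpose: "The study will inform medical decision-making about the need for (and timing of) re-calibration of radiation dosimetry plans". Section 9.5, headed "To be conducted within each stratum", turns to this in item 6. That item first asks whether changes in the volume variables are clinically relevant and, if so, undertakes to "identify the earliest time point at which re-calibration is warranted". It concedes that "it may not be possible to identify a single 're-calibration solution' for all patients in a particular stratum" and then gives the working rule: "we will attempt to identify the earliest scan time point at which the majority of patients have clinically important changes in tumor volume or location". The change must also lead to over-shoot of the target, a higher dose to normal organs, or both.

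On size, section 9.2 states "The study will enroll 30 patients in each stratum", and the overview gives "30 patients per treatment site for a total of 120 patients".

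Item 6 does not say what is reported if no scan reaches a majority. Items 1 to 3 summarise continuous variables at each scan, item 4 describes dose distributions, and item 5 fits patient-clustered longitudinal models. None of them reports the proportion of patients with clinically important change at each scan, or the scan at which a patient first shows it.

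**The concern.** The aim and the rule are different quantities. The aim concerns when re-calibration starts to be justified. The rule returns the scan at which the count of changed patients passes half the stratum. This matters in two situations.

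- **A large minority changes.** The rule returns nothing, although a third or more of the stratum may have met the study's own criterion.
- **A majority changes gradually.** The rule returns a scan close to the median patient's onset, and the patients who changed earlier do not show in the result.

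Item 6 is the only planned analysis that converts the measurements into a statement about re-calibration timing. What is at stake is how well the study can inform the decision named in section 9.2. The point is about which quantity is derived, not about the cut-off for clinical importance.

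**Working it through.** **Inputs.** 30 patients per stratum and four strata (section 9.2); weekly measurement over 7 to 8 weeks (section 9.4), with 7 scans used here; the majority rule (section 9.5 item 6). The documents give neither the true share of patients who change nor the timing of change, so both are assumed over a range.

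**The plan's own figure.** 4 × 30 = 120, which matches the stated total. No power or precision basis is given for the 30, so there is nothing further to reproduce.

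**Step 1: what a majority means.** More than half of 30 is more than 15, so at least 16. A result of 15/30 (50%) names no scan.

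**Step 2: chance that a stratum names any scan.** Let *p* be the true share changed by the last scan. With independent patients, complete scans and change that persists, the number changed is X ~ Binomial(30, *p*), and

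P(X ≥ 16) = Σ from x = 16 to 30 of C(30, x) pˣ (1 − p)³⁰⁻ˣ.

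| True share p | Expected number changed, 30p | P(a scan is named) | P(none named) |
|---|---|---|---|
| 30% | 9.0 | 0.6% | 99.4% |
| 35% | 10.5 | 3.0% | 97.0% |
| 40% | 12.0 | 9.7% | 90.3% |
| 45% | 13.5 | 23.1% | 76.9% |
| 50% | 15.0 | 42.8% | 57.2% |
| 60% | 18.0 | 82.5% | 17.5% |

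This step needs no assumption about when change starts.

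**Step 3: how many changed before the named scan.** Let C(k) be the cumulative number changed at scan k. The named scan k* is the first with C(k*) ≥ 16, so C(k* − 1) ≤ 15. The share already changed at an earlier scan is therefore at most 15/30 = 50%. It is 0 if the first scan already shows a majority. Between those limits it depends on onset timing. The following are averages over strata that named a scan, from 20,000 simulated strata of 30 with 7 complete weekly scans and persistent change:

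| Assumed onset pattern | Mean share changed before the named scan |
|---|---|
| Uniform over 7 weeks; 60%, 80% or 100% ever change | 45%, 44%, 43% |
| Bell-shaped around week 4 (5, 10, 20, 30, 20, 10, 5%) | 36% |
| 10% per week except 40% in week 4 | 30% |
| 60% in week 1, then 20, 10, 5, 5% | 8% |
| 85% in week 4, 5% in each of weeks 3, 5 and 6 | 5% |

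**Step 4: what a cumulative proportion would show.** Exact (Clopper-Pearson) 95% intervals at n = 30:

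| Changed | Proportion | 95% interval | Majority rule returns |
|---|---|---|---|
| 9/30 | 30% | 14.7% to 49.4% | nothing |
| 12/30 | 40% | 22.7% to 59.4% | nothing |
| 15/30 | 50% | 31.3% to 68.7% | nothing |
| 16/30 | 53% | 34.3% to 71.7% | a scan |

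The results 15/30 and 16/30 are statistically almost the same, yet one produces a time point and the other does not.

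**The case against.** The strongest reply is that item 6 is a modest, openly stated summary in a descriptive pilot. It says the team will attempt the search and admits that one answer may not fit everyone. Re-calibration timing is not among the aims in section 3.0 or the objectives in section 9.3, and items 1 to 5 already report much of the spread. Any median-type time has some patients before it. All of this is fair and limits the weight of the point. It does not remove it, because none of the other items gives the proportion changed or the time of first change, and describing that distribution suits a descriptive study.

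Four stronger readings are tempting, and the documents do not support them.

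- **Any named week is late for nearly half the patients.** Half is a ceiling. The 43% to 45% figure needs uniform onset, and concentrated onset gives 5% to 8%. Nor does the rule systematically name a late week.
- **The head and neck stratum would return nothing 97% of the time.** Section 2.0 says "about 35% of patients with head and neck cancers experience >10% weight loss", but that is weight loss. Item 6 concerns tumor volume or location with a dosimetric consequence. Section 2.0 also cites a median GTV reduction of 44.3% in NSCLC, a 69.5% reduction in head and neck cancer and median regression of 69% to 79% in cervical cancer, so majorities are plausible. They are not assured, because shrinkage alone does not meet item 6. The small proton study cited there (8 patients) found CTV coverage adequate once motion was handled by 4D planning.
- **No majority will be read as re-calibration not being warranted.** The text does not say this, and item 6 asks about clinical relevance separately. The gap is that it says nothing about this outcome.
- **Patients would be treated on outdated plans.** The Radiotherapy Planning text in section 6.5 lets the treating physician create a new plan when the original is no longer optimal. The consequence is for the study's inference.

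**Conclusion.** The concern holds in this form: the majority rule does not measure what item 6 sets out to find. A stratum in which up to half the patients change names no time point. The chance of naming one is only 0.6% to 42.8% across true shares of 30% to 50%. Where a scan is named, from 0 to 50% of patients can already have changed at an earlier one.

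The first result rests on 30 independent patients with complete scans and persistent change. The second depends on onset timing, which the documents do not give. The scan schedule (CT up to weekly, or as few as 3 MR scans, sections 6.6 and 9.2) means that fewer than 30 patients may be assessable in a given week, so these figures describe the favourable case of full data.

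This is an inexpensive improvement to a secondary but decision-facing analysis. It is not a defect that undermines the study's descriptive aims.

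**What to change.** In section 9.5 item 6:

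1. Derive for each patient the first scan with clinically important change, using whatever definition the study adopts.
2. Report per stratum the cumulative proportion changed by scan, with exact 95% intervals where follow-up is complete, and the ever-changed proportion. Treat onset as lying between the last unchanged scan and the first changed one, and treat patients who never change as censored at their last scan. Where censoring or unequal scan spacing matters, use an interval-censored estimate with its own interval.
3. Keep the majority scan as one row of that table.
4. State that the absence of a majority is not by itself evidence that re-calibration is unwarranted.

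Times by which 25% and 50% of patients have changed are optional. They will be imprecise at n = 30 and coarse where a patient has only 3 MR scans.

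The cost is a wording change and one extra table or curve per stratum from data already collected. The downside is that readers get a distribution instead of a single week. The derivation also needs a per-patient definition of clinically important change, but so does the present majority rule.
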